#### Age and gender-similar OA patients must meet ALL the following criteria to be included in study:

- > 2 recorded OA-related diagnosis codes:
- Code list
- >65 years
- Enrolled in the data source for at least 365 days prior index procedure (baseline period)

#### 5.2.2 Exclusion criteria

THA patients meeting any of the following during the 365-day baseline period will be excluded from the study:

- Diagnosis code for acute or chronic heart failure
- TKA or THA surgery (primary or revision)
- Concurrent (with index procedure) diagnosis of hip fracture

# Age and gender-similar OA patients meeting any of the following during the 365-day baseline period will be excluded from the study:

- Diagnosis of acute or chronic heart failure
- TKA or THA surgery (primary or revision)
- Arthroscopic surgery

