# 3. Rationale and Background

It is estimated that the incidence of joint replacement is over 1 million total hip and total knee replacement procedures each year in the United States. With the aging of the "baby boomers," higher rates of diagnosis and treatment of advanced arthritis, and growing demand for improved mobility and

quality of life, the annual procedure volumes are projected to increase considerably in the future, making joint replacements the most common elective surgical procedures in the coming decades. The prevalence of total hip replacement in the United States was projected by Kremers et al in a 2015 publication. The authors reported the 2010 prevalence of total hip replacement in the U.S. population was 0.83% for the overall population and 2.34% in those 50 years of age and older. The prevalence of hip replacement was higher among women (0.93%) than among men (0.72%) and increased with age, reaching 1.49%, 3.25%, and 5.26% at sixty, seventy, and eighty years, respectively. These estimates corresponded to 2.5 million individuals (1.4 million women and 1.1 million men) with total hip replacement in 2010.

A study published by Gillam et al. in 2017 described a retrospective cohort study using data from the Australian Government Department of Veterans' Affairs health claims database on patients who received conventional THA for osteoarthritis between 2004 and 2012. The MoM THAs were classified into groups: Articular Surface Replacement (ASR) XL Acetabular System, other large-head (LH) (> 32 mm) MoM, and small-head (SH) ( $\leq$  32 mm) MoM. The primary outcome was hospitalization for heart failure after THA and included 4,019 patients with no history of heart failure (56% women). Men with an ASR XL THA had a higher rate of hospitalization for heart failure than men with MoP THA (hazard ratio (HR) = 3.2, 95% CI: 1.6–6.5). No statistically significant difference in the rate of heart failure was found with the other LH MoM or SH MoM compared to MoP in men. There was no statistically significant difference in heart failure rate between exposure groups in women.

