## 4.2 Research Objectives

#### 4.2.1 Primary objective(s):

- To estimate the incidence and evaluate the risk of heart failure among patients undergoing MoM arthroplasties of the hip compared with those with alternative types of arthroplasties (non-MoM)
- To estimate the incidence and evaluate the risk of heart failure among patients undergoing MoM arthroplasties of the hip compared with an age and gender similar Osteoarthritis cohort without arthroplasty

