#### Exclusions for both study groups:

- Patients who have enrolled in Medicare due to disability
- Patients who have enrolled in Medicare due to end stage renal disease (ESRD)
- Patients enrolled in a HMO

• Patients with an orthopedic procedure requiring metal implants (e.g. knee, hip, shoulder, trauma plates, and spine) during baseline period

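### The OA comparator is screened for earlier arthroplasty over only 365 days, and the protocol text gives it no index date of its own

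*Protocol*

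**What the plan says.** Section 4.2.1 sets MoM patients against an "age and gender similar Osteoarthritis cohort without arthroplasty" as the second co-primary comparison; the synopsis says the same.

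The criteria that build this cohort are in Sections 5.2.1 and 5.2.2:

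- Entry requires repeated OA codes ("> 2 recorded OA-related diagnosis codes") and a run-in: "Enrolled in the data source for at least 365 days prior index procedure (baseline period".
- The exclusion list opens with "Age and gender-similar OA patients meeting any of the following during the 365-day baseline period will be excluded from the study". One item on it is "TKA or THA surgery (primary or revision".
- The implant exclusion for both study groups has the same limit: "Patients with an orthopedic procedure requiring metal implants (e.g. knee, hip, shoulder, trauma plates, and spine) during baseline period".

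The synopsis identifies the index procedure as the elective primary THA. Section 5.2.1 defines an index date only in the THA list, and Section 5.3.3.1 treats index date and implantation as the same thing. Section 5.4.2 starts every patient's person-time 30 days after the index date.

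**The concern.** There are two gaps, both affecting a co-primary comparison.

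First, the written criteria do not produce the cohort that the objective names. Never having had an arthroplasty and having had none in the past year are different conditions. A patient whose hip or knee was replaced 13 months before index, and who still has OA codes, enters as an unexposed control.

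Second, the enrollment criterion cannot be applied to OA patients as written, because it refers to an operation they have not had. Baseline covariates, the heart failure exclusion, the 30-day exclusion and the start of person-time all hang on that date. Two programmers could choose different dates (first OA code, qualifying OA code, a date matched to surgery) and obtain different hazard ratios, and one of these choices builds a bias into the comparison.

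**Working it through.** **Is earlier arthroplasty caught anywhere else?** Section 5.2 ends follow-up at a new TKA or THA, which deals with arthroplasty after index. Section 5.3.1 lists the OA group by name only. No criterion covers arthroplasty or implants before the 365-day window. The study period opens on October 1, 2004, and index dates run from October 1, 2005 to December 31, 2017. Available look-back therefore runs from 365 days for the earliest index dates to about 13.2 years for the latest, and the criteria use 365 days throughout.

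**Is an OA index date given anywhere?** Section 5.2 gives a calendar window for index dates but no OA index event. Elsewhere the index date is tied to THA or to implantation.

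The protocol states no figure to reproduce on this point. The two calculations below are illustrations.

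**Size of dilution.** Let *c* be the share of controls who carry the exposure. The control rate is then λ(1 − c) + λ·c·HR, so

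HR observed = HR / (1 + c(HR − 1)).

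For *c*, take the hip replacement prevalence in Section 3, "reaching 1.49%, 3.25%, and 5.26% at sixty, seventy, and eighty years, respectively", at 70 and 80 years. These are general-population figures; an OA cohort could be higher. As a worst case, treat every carrier as having a MoM hip.

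| True HR (assumed) | c = 3.25% | c = 5.26% |
|---|---|---|
| 1.2 | 1.2/1.0065 = 1.192 | 1.2/1.0105 = 1.188 |
| 1.5 | 1.5/1.0163 = 1.476 | 1.5/1.0263 = 1.462 |
| 3.2 | 3.2/1.0715 = 2.99 | 3.2/1.1157 = 2.87 |

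Most carriers would not have MoM. In the linkage study cited in Section 3, MoM made up 53,529 of 53,529 + 482,247 = 535,776 hips, or 10.0%. If that share held here (assumption), *c* would be about 0.33% to 0.53%. At 0.53%, an HR of 1.2 becomes 1.2/1.0011 = 1.199.

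**Size of a misplaced start.** Suppose the index were the first OA code while entry required a later one. Let *F* be mean follow-up after the completing code, and *g* the person-time counted before it, taken as free of events. Under no effect the OA rate is λF/(F + g), so

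spurious MoM-versus-OA HR = (F + g)/F.

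| F (years, assumed) | g = 0.25 | g = 0.5 | g = 1 |
|---|---|---|---|
| 3 | 1.08 | 1.17 | 1.33 |
| 5 | 1.05 | 1.10 | 1.20 |
| 8 | 1.03 | 1.06 | 1.13 |

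These are upper bounds. A patient who developed heart failure between the two codes and then received the second would still contribute an event. Also, person-time starts 30 days (0.082 years) after index. If the gap is measured from the first code itself, the 5-year figures fall to (5 + 0.25 − 0.082)/5 = 1.03 and (5 + 1 − 0.082)/5 = 1.18.

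For scale, two of the background studies report an adjusted HR of 0.901 and odds ratios of 0.91 to 0.93. A start-date artefact of this order could create or hide effects of that size.

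**The case against.** The intent is clear from the label, and Section 5.2 repeats that the OA group has no arthroplasty. The study design graphic is not shown, and a statistical analysis plan may exist; either could define the OA index date. That limits the claim to the protocol text. It does not rescue the enrollment criterion, which names a procedure this cohort does not have, or the mismatch between the objective and the exclusion window.

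Four stronger readings are tempting, and the document does not support them.

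- *Immortal time is built into the design.* No section uses the first OA code as index. If the index were the date on which the last required code is recorded, no such time would arise. The bias depends on how the gap is filled.
- *Contamination is heavy.* The only prevalence figures in the protocol are the general-population hip figures used above. Any larger share would need an unsourced prevalence, and counting knees would not measure MoM exposure.
- *Contamination pulls the result toward the null.* That would follow if the carriers had MoM hips. Carriers of other prostheses lack the exposure. If patients selected for surgery are healthier, their presence among controls could raise the MoM hazard ratio instead.
- *Surgery versus no surgery makes the comparison uninterpretable.* The other co-primary, MoM against non-MoM, addresses the bearing. Using two comparators is a legitimate choice.

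Calendar year and index year are listed variables and propensity adjustment is planned, so calendar imbalance can be handled once an index date exists. The 365-day window also applies to the THA groups. Lengthening it for OA patients alone would make ascertainment unequal, and the fix has to respect that.

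**Conclusion.** The point holds. As written, the OA criteria admit patients with an older hip or knee prosthesis into a cohort meant to have none, and the protocol text gives that cohort no usable index date although its eligibility and follow-up depend on one.

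The index date is the more important half. Under one plausible choice the artefact could reach an HR of 1.05 to 1.20 with no true effect, assuming a counted gap of 0.25 to 1 year, 5 years' mean follow-up and no events in the gap. The look-back half is probably small: an HR of 1.2 falls only to about 1.19 in the worst case at the protocol's own hip prevalence, and the direction of the net effect is not established. Neither figure estimates the actual bias. Both halves should be settled before the analytic file is built.

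**What to change.** 1. In Section 5.2.1, replace the index procedure for OA patients with an assigned index date on which every entry criterion, including the required OA codes, is already met. One way is to sample, at each MoM surgery date, OA patients of the same age and sex who are eligible by then, and give them that date. Other assignments that do not depend on later codes would also serve. Count baseline, the heart failure exclusion, the 30-day exclusion and person-time from this date, and amend Section 5.3.3.1 so that index date no longer means implantation for this cohort.

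2. In Section 5.2.2, exclude OA patients with any THA, TKA, metal-implant or joint-prosthesis-status code in all available data before index, from October 1, 2004. Apply the same look-back for prior arthroplasty and implants to both THA groups.

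3. In Section 5.6, state that look-back length varies with index year and that implants placed before the data begin may be missed.

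A non-MoM THA versus OA comparison would help to read the result against surgery itself, but it is optional.

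The cost is programming on data already held. The OA pool becomes somewhat smaller, and THA patients with an earlier implant are lost.

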#### 5.2.1 Inclusion criteria

THA patients must meet ALL the following criteria to be included in study:

- Elective, primary THA performed in inpatient setting (first occurrence is the index date)
- >65 years
- Enrolled in the data source for at least 365 days prior to index procedure (baseline period)

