#### 5.4.3 Risk of Heart Failure Associated with MoM Implants

Cox proportional hazards regression will be performed to determine HRs of heart failure with 95% Cis in MoM implants versus non-MOM implant and MoM implants versus RA patients without arthroplasty. Propensity score matching or stratification will be used to control for confounding.

If a significantly higher risk of heart failure is identified for patients with MoM implants, Cox proportional hazards regression will be conducted to determine risk factors for a diagnosis of heart failure.

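### Baseline arthroscopic surgery excludes OA controls but not THA patients, so the two arms of the second co-primary comparison pass different eligibility screens, with no reason given

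*Protocol*

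**What the plan says.** Protocol section 4.2.1 sets the second co-primary objective as the risk of heart failure after MoM hip arthroplasty "compared with an age and gender similar Osteoarthritis cohort without arthroplasty".

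Section 5.2.2 gives three exclusion lists:

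- **THA patients**, introduced by "THA patients meeting any of the following during the 365-day baseline period will be excluded from the study": heart failure; "TKA or THA surgery (primary or revision"); hip fracture concurrent with the index procedure.
- **OA patients**, same 365-day window: heart failure; the same TKA/THA item; and "Arthroscopic surgery". The joint is not named.
- **Both groups**: among other items, "Patients with an orthopedic procedure requiring metal implants (e.g. knee, hip, shoulder, trauma plates, and spine) during baseline period".

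The protocol does not say why arthroscopy is on the OA list alone. The exclusions in the synopsis do not mention it.

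**The concern.** A cohort comparison should apply the same baseline screen to both arms unless an item can only occur in one of them. The hip-fracture item is of that kind, because it is tied to the index operation. Arthroscopy is not: it is an event of the baseline year that a future MoM patient or an OA control may equally have had. The objective does not require the item either. The control has to be without arthroplasty, and the TKA/THA and metal-implant exclusions already address that in the baseline year.

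What is at stake is comparability in a co-primary hazard ratio. If patients with a recent arthroscopy carry a different heart failure risk, removing them from one arm moves that arm's rate. The shift comes from the eligibility rule, so a larger sample does not reduce it.

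**Working it through.** **1. Compare the lists.** There are three baseline surgery exclusions in section 5.2.2.

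| Baseline surgery | THA (MoM) arm | OA arm |
|---|---|---|
| TKA or THA | excluded | excluded |
| Orthopedic procedure requiring metal implants | excluded | excluded |
| Arthroscopy | kept | excluded |

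Two are shared and one is one-sided.

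**2. Can adjustment repair it?** Section 5.4.3 states: "Propensity score matching or stratification will be used to control for confounding". Arthroscopy is not among the variables in sections 5.3.2.1 to 5.3.2.4. Adding it would not help: by construction no OA control has a baseline arthroscopy, so MoM patients who do would have no counterpart to be matched with or stratified against.

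**3. Size.** The protocol states no figure for this, so there is none to reproduce. Let p be the share of otherwise eligible OA controls with a baseline arthroscopy, and r their heart failure rate relative to other OA patients, after adjustment. The protocol gives neither, so both are assumptions. Setting the rate among the remaining controls to 1, the control rate with arthroscopy patients kept is (1 − p) + p·r, and without them it is 1. The control rate is the denominator of the hazard ratio, so dropping these patients from the OA arm alone multiplies the ratio, approximately, by

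factor = (1 − p) + p·r.

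| p | r = 0.5 | r = 0.7 | r = 1.0 | r = 1.2 |
|---|---|---|---|---|
| 1% | 0.995 | 0.997 | 1.000 | 1.002 |
| 2% | 0.990 | 0.994 | 1.000 | 1.004 |
| 5% | 0.975 | 0.985 | 1.000 | 1.010 |
| 10% | 0.950 | 0.970 | 1.000 | 1.020 |

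For example, p = 5% and r = 0.7 give 0.95 + 0.05 × 0.7 = 0.985; p = 5% and r = 1.2 give 0.95 + 0.05 × 1.2 = 1.010.

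This measures the plan against keeping arthroscopy patients in both arms. Measured against excluding them from both, the formula is the same, with p replaced by the share of MoM patients who had one (and r taken to be the same in that arm).

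**4. Scale against random error.** Section 5.3.4 gives 18,521 MoM patients. The Medicare study described in section 3 reports 8.73% cardiac failure at four years after MoM THA. Borrowing that figure, 18,521 × 0.0873 ≈ 1,617 events. With as many events among controls (assumed), SE(log HR) ≈ √(2/1,617) = 0.035. Then:

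- factor 0.985: −ln(0.985)/0.035 ≈ 0.43 SE
- factor 1.010: ln(1.010)/0.035 ≈ 0.28 SE
- factor 0.975, the largest shift in the table for p up to 5%: ≈ 0.72 SE
- factor 0.950, the corner of the table: ≈ 1.5 SE

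The event count is a rough guide only. It comes from a different cohort, selected for at least five years of follow-up, and not from this protocol's endpoint.

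**The case against.** The strongest reply accepts the asymmetry and disputes its consequence.

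- **A reader might infer that only the control arm loses patients recently judged fit for elective surgery.** The text does not support that. The THA arm also loses patients with a baseline TKA or THA, and both arms lose those with metal-implant procedures; many of these operations are elective. Only the arthroscopy item is one-sided. This stands.
- **A reader might infer that the rule always hides harm from MoM implants.** That requires r below 1, and the protocol has no data on it. At r = 1 there is no shift, and above 1 the direction reverses. This stands.
- **The propensity score may absorb much of the difference.** If the path is general fitness, the listed covariates (age, BMI, Charlson and Elixhauser measures, hypertension, diabetes, pulmonary disease, arrhythmia) would capture part of it, so the r that matters may lie nearer 1 than a crude ratio. This stands as to size. It does not make the eligibility rules equal.
- **A larger imbalance is built into the comparison.** Entry to the THA arm requires "Elective, primary THA performed in inpatient setting (first occurrence is the index date"), so every MoM patient was selected for elective surgery, while OA controls were not. Harmonising one exclusion barely changes that. This is true, but it is no reason to keep a second, avoidable difference.

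**Conclusion.** The point holds as a minor one. In the MoM versus OA comparison, the arms pass different baseline screens on arthroscopy, without a stated reason and in a way that covariate adjustment cannot undo. This is read directly from section 5.2.2 and rests on no assumption.

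The effect on the hazard ratio is conditional. It is nil if arthroscopy patients have the same adjusted heart failure risk as other OA patients, downward if their risk is lower and upward if it is higher. For assumed p up to 5% and r between 0.5 and 1.2, the factor lies between 0.975 and 1.010, less than one standard error on the rough scale above. The documents support neither a claim that the bias runs in a known direction nor a claim that it is large. The MoM versus non-MoM comparison is unaffected, since both of its arms use the THA list.

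**What to change.** Apply one rule to both arms in section 5.2.2, in either of two ways:

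- move the arthroscopy item to the list of exclusions for both study groups, so that it also binds MoM and non-MoM patients; or
- delete it from the OA list.

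If it is kept for the first option, name the joint or joints meant. If the sponsor has a reason for the one-sided rule, the fallback is to state it and add to section 5.4.4 a sensitivity analysis with the rule harmonised.

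The cost is one line of eligibility text and one line in the attrition program, with no new data. Moving the item makes the THA cohorts slightly smaller. Deleting it makes the OA cohort slightly larger, and may add some controls whose follow-up ends early, because section 5.2 stops follow-up at a new TKA or THA. The attrition counts already planned in section 12 would show how many patients are involved.

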#### Exclusions for both study groups:

- Patients who have enrolled in Medicare due to disability
- Patients who have enrolled in Medicare due to end stage renal disease (ESRD)
- Patients enrolled in a HMO

• Patients with an orthopedic procedure requiring metal implants (e.g. knee, hip, shoulder, trauma plates, and spine) during baseline period

#### 5.3 Variables

Final code lists for all variables will be included in the study report.

#### 5.3.1 Primary Independent Variable(s) – Exposure Groups

- Group 1: Metal-on-Metal total hip arthroplasty
  - o ICD-9: 00.75, hip bearing surface, metal-on-metal
  - o ICD-10 Codes:
    - OSRR01Z, Replacement of Right Hip Joint, Femoral Surface with Metal Synthetic Substitute, Open Approach
    - OSRS01Z, Replacement of Left Hip Joint, Femoral Surface with Metal Synthetic Substitute, Open Approach
    - OSRS019, Replacement of Left Hip Joint, Femoral Surface with Metal Synthetic Substitute, Cemented, Open Approach
    - OSRS01A, Replacement of Left Hip Joint, Femoral Surface with Metal Synthetic Substitute, Uncemented, Open Approach
- Group 2: Non-Metal-on-Metal total hip arthroplasty
  - o ICD-9 Codes
    - 00.74, hip bearing surface, metal-on-polyethylene (MoP)
    - 00.76, hip bearing surface, ceramic-on-ceramic (CoC)
    - 00.77, hip bearing surface, ceramic-on-polyethylene (CoP)
  - o ICD-10 Codes:
    - OSRR03Z, Replacement of Right Hip Joint, Femoral Surface with Ceramic Synthetic Substitute, Open Approach
    - OSRS03Z, Replacement of Left Hip Joint, Femoral Surface with Ceramic Synthetic Substitute, Open Approach
    - OSRS039, Replacement of Left Hip Joint, Femoral Surface with Ceramic Synthetic Substitute, Cemented, Open Approach
    - OSRS03A, Replacement of Left Hip Joint, Femoral Surface with Ceramic Synthetic Substitute, Uncemented, Open Approach
- Age and gender-similar OA patients

Introduced in October 2005, ICD-9 bearing surface code identifiers (00.74 for Metal on p, 00.75 for M-M, 00.76 for C-C, 00.77 C-PE) are optional modifiers that can be reported in conjunction with the primary procedure code for total hip arthroplasty. A limitation on this data is that it has been shown to have both under-coding and misclassification when coded.

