#### 5.4.4 Sensitivity Analyses

- Limit outcome to hospitalization for heart failure
- Stratification by ICD-9 and ICD-10 codes (ICD-10 codes may be improved for ascertaining both MoM prostheses use and for heart failure as compare to ICD-9 codes)
- Stratification for non-MoM comparison (exclude MoP from the comparator group)

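### For ICD-10-coded index procedures the exposure is set by femoral-surface material alone, so a metal-on-polyethylene hip that is a comparator under ICD-9 meets the metal-on-metal definition

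*Protocol*

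**What the plan says.** Protocol section 5.3.1 defines the two arthroplasty groups separately for each coding system.

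- **ICD-9.** Group 1 is "ICD-9: 00.75, hip bearing surface, metal-on-metal". Group 2 is "00.74, hip bearing surface, metal-on-polyethylene (MoP"), together with 00.76 (ceramic-on-ceramic, CoC) and 00.77 (ceramic-on-polyethylene, CoP). Each code names both bearing surfaces.
- **ICD-10, Group 1.** There are four codes, all for a metal femoral surface. The right hip has one, ending in 01Z. The left hip has three, ending in 01Z, 019 and 01A. The first of these reads "OSRS01Z, Replacement of Left Hip Joint, Femoral Surface with Metal Synthetic Substitute, Open Approach"; the other two are its cemented and uncemented variants.
- **ICD-10, Group 2.** There are four codes with the same pattern for ceramic, beginning with "OSRR03Z, Replacement of Right Hip Joint, Femoral Surface with Ceramic Synthetic Substitute, Open Approach".

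Index dates run from October 1, 2005 to December 31, 2017 (section 5.2), and both coding systems feed the same groups. Section 5.4.4 plans a sensitivity analysis stratified by coding system, on the ground that "ICD-10 codes may be improved for ascertaining both MoM prostheses use and for heart failure", and another that drops MoP from the comparator. Section 5.3 says that final code lists will appear in the study report.

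**The concern.** Bearing type is the study's main variable, and Group 1 is the exposed arm of both co-primary comparisons. None of the eight ICD-10 descriptors mentions the acetabular side or the liner, so none says what the femoral surface moves against. The meaning of exposed and unexposed therefore changes partway through accrual: from the bearing couple to the material of one surface, and from a comparator that includes MoP to one that does not.

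A study that asks whether MoM hips carry extra heart-failure risk could then miss or understate a real difference because comparator-type hips sit in the exposed arm. The planned stratification could also be misread. If the ICD-10 stratum shows a weaker association, the protocol's own remark invites the reader to treat it as the better-measured one.

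**Working it through.** **Step 1. Classify each bearing couple by the listed descriptors.**

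| Bearing couple | ICD-9-coded | ICD-10-coded |
|---|---|---|
| MoM | Group 1 (00.75) | Group 1 (metal femoral surface) |
| MoP | Group 2 (00.74) | Group 1 (metal femoral surface) |
| CoC | Group 2 (00.76) | Group 2 (ceramic femoral surface) |
| CoP | Group 2 (00.77) | Group 2 (ceramic femoral surface) |

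Only the MoP row changes group. Codes for a metal femoral surface are 4 of 4 in ICD-10 Group 1 and 0 of 4 in ICD-10 Group 2. The sensitivity analysis that removes MoP from the comparator therefore has nothing to remove in the ICD-10 stratum.

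**Step 2. Compare the sides.** In each group the left hip has suffixes Z, 9 (cemented) and A (uncemented), and the right hip has Z only. Judged against the protocol's own left-hip list, 2 of 3 right-hip codes are absent in Group 1 and 2 of 3 in Group 2.

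**Step 3. Share of the index window.** The documents do not date the change to ICD-10. Assuming October 2015, it covers 27 of the 147 index months: 27/147 = 18.4%. Moving the assumed date to October 2014 or October 2016 gives 26.5% or 10.2% of the window.

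**Step 4. Dilution within the ICD-10 stratum (illustration).** Let p be the share of labelled MoM patients who are truly MoM, and assume that the rest have the comparator's hazard. Then, approximately, observed HR = p × true HR + (1 − p) × 1. For an assumed true HR of 1.5:

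- p = 0.50: 0.50 × 1.5 + 0.50 = 1.25
- p = 0.10: 0.10 × 1.5 + 0.90 = 1.05

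With 1:1 allocation, 80% power and two-sided 5% (Schoenfeld's formula; all three are assumptions), the events needed rise from 191 at HR 1.5 to 631 at HR 1.25.

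**Step 5. Effect on the pooled HR (illustration).** Let e be the weight of the ICD-10 era in Group 1. At the worst case above, pooled HR = (1 − e) × 1.5 + e × 1.05.

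- Weighting by headcount, with 40% of Group 1 from that era: 0.6 × 1.5 + 0.4 × 1.05 = 1.32.
- A Cox estimate is driven by events, and under the October 2015 assumption these patients have at most about 2.75 years to June 30, 2018. Assume mean follow-up of 1.5 years against 5 years, with person-time standing in for events. A 40% headcount share then gives e = (0.4 × 1.5)/(0.4 × 1.5 + 0.6 × 5) = 0.60/3.60 = 16.7%, and the pooled HR is 1.5 − 0.167 × 0.45 = 1.425.
- With an 18% headcount share, e = 0.27/4.37 = 6.2% and the pooled HR is 1.5 − 0.062 × 0.45 = 1.47.

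**The case against.** Much can be said in the protocol's favour, and part of it stands.

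- **The stratification by coding system is already planned.** It would give an ICD-9-only estimate and so expose the problem. Calendar year and year of index date are listed variables, available to the propensity score. This limits the harm. It does not repair the primary result, which still pools both eras, and no adjustment for year recovers the bearing couple.
- **Final code lists are deferred.** The protocol nevertheless prints a specific list. Settling the exposure definition only in the report would leave it open until after the data have been seen.
- **A coding limitation is acknowledged.** The sentence in section 5.3.1 follows the description of the optional ICD-9 modifiers. It does not say that the ICD-10 entries lack the second surface.

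A reader might also infer more than the documents support:

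- *That MoP is shut out of the comparator altogether.* It is not: 00.74 admits MoP for every ICD-9-coded procedure, 120 of 147 index months under the October 2015 assumption.
- *That replacements of the femoral side alone enter Group 1.* Section 5.2.1 requires a primary total hip arthroplasty, which may screen them out. The code list for that requirement is not shown, so their entry is not established.
- *That the missing right-hip codes bias the HR.* The omission is the same in both groups and mainly loses cases.
- *That the HR must move toward 1.* This holds only if MoP patients have about the hazard of the other non-MoM patients. If their residual risk differs, the bias could go either way. Against the osteoarthritis cohort, contamination pulls the estimate toward the HR for MoP hips, whatever that is.
- *That the pooled HR could be as low as 1.32.* That figure weights by headcount and overstates the effect when the later era has short follow-up.

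**Conclusion.** The point holds for ICD-10-coded index procedures. By the protocol's own descriptors the same MoP hip is a comparator under one coding system and exposed under the other, and the ICD-10 comparator contains no MoP. This follows from section 5.3.1 alone and needs no assumption. Nothing else in the protocol corrects it, and the listed codes do not support the suggestion in section 5.4.4 that ICD-10 may identify MoM use better.

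The size cannot be fixed from the documents: the changeover date, the share of ICD-10-labelled MoM patients who are truly MoM, and that era's share of events are all absent. Under the assumptions shown, a true HR of 1.5 would appear as 1.05 to 1.25 within the ICD-10 stratum. The pooled effect is smaller, with a worst case of about 1.43 to 1.47 under the follow-up-weighted illustrations. The right-hip gap is a secondary matter of lost cases. The inconsistency should be corrected before the analysis file is built, because it concerns the definition of the exposed group.

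**What to change.** 1. Make the ICD-9 stratum the primary analysis: exposure from 00.74 to 00.77 reported with a primary total hip arthroplasty code, an index window ending at the change to ICD-10, and outcome follow-up still to June 30, 2018. State the changeover date in the protocol.
2. Report ICD-10-era index procedures as a sensitivity analysis. Admit a code to Group 1 only if it identifies a metal-on-metal couple, class MoP as non-MoM, and give right and left hips the same suffix set. Where the available codes cannot identify the couple, do not label those patients MoM. The documents do not show whether suitable codes exist, so this must be checked first.
3. Remove or qualify the section 5.4.4 remark on improved MoM ascertainment, and say that dropping MoP from the comparator is informative only where MoP can be identified.

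The cost is wording in the code lists, the index window (synopsis and section 5.2) and section 5.4.4. The most recent index procedures leave the primary analysis; they have the shortest follow-up. The under-coding and misclassification that the protocol admits for the ICD-9 modifiers remain and should still be reported as a limitation.
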